The eligible PIBD cases will comprise all incident cases of PIBD over the last decade, we will not follow patients up beyond 01/01/2020 due to changes in patient health behaviour and primary care interactions due to COVID-19. We will extract sociodemographic details for all these cases and matched controls (described below). Sociodemographic data will comprise by age group, gender, ethnicity, and socioeconomic status. Ethnicity will be categorised as follows to be consistent with the UK official census categories: White, Asian, Black African/Caribbean, Mixed, and Other. The index of multiple deprivation (IMD) will be used as a measure of socioeconomic status. This is derived from patient postcode at the point of data extraction.

Stream 1: Definition of matched controls without IBD

We will match each incident case of PIBD with controls (children without IBD) using propensity score matching (matching on the sociodemographic variables list above and matching within primary care practice if numbers allow). People with a known diagnosis of irritable bowel syndrome (IBS) will be excluded from the potential pool of controls. We will compare the incidence of new onset mental health conditions in PIBD and controls using a similar approach to that used by Butwick et al. (2019) in their paper exploring psychiatric disorders in a

PIBD cohort in Sweden.(9) The mental health conditions to be examined are listed in table 1 although there is scope to add to or modify these in discussion with the study authors. For a composite 'any psychological condition' outcome (see Table 1), risk will be stratified by age of PIBD onset and sex.

We will then go beyond the analysis of the Swedish study to estimate the cumulative risk of the 'any psychological condition' composite outcome in PIBD patients compared with controls. This will provide a unique, robust, estimate of the overall mental health burden (prevalence) in PIBD.

Condition	Description
Primary outcomes	
Any psychological condition	A composite of all the chronic psychiatric conditions listed below* (depression, anxiety, eating disorders, body image disorder, attention-deficit disorder, behavioural disorders, adjustment disorder, acute stress disorder, and post-traumatic stress disorder)
Depression	Major recurrent depression or treated depressive episode
Anxiety	Non-phobia related anxiety episodes or disorder
Secondary outcomes	
Self-harm	Any coded episode of deliberate self-harm of any type

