Suicide attempt	Any episode of suicide attempt and suicide related codes, including deliberate medication overdose
Other chronic psychiatric conditions	Eating disorders, body image disorder, attention-deficit disorder (ADHD), behavioural disorders, adjustment disorder, acute stress disorder, schizophrenia, bipolar disorder and post-traumatic stress disorder (PTSD)
Others	Problems with sleep

*this excludes conditions which are potentially single events i.e. self-harm or suicide attempt. (See Appendix 1 – Table s3 for Read Codes and SNOMED Codes

for mental health conditions, Table s4 for mental health condition algorithms and Table s5 for WHO ICD-10 mental health conditions).

Stream 1: Incidence of mental health conditions

The study will report the incidence of each mental health condition overall in the PIBD cases and controls, and adjusted hazard ratios to test the association between PIBD and risk of the same mental health conditions. Within the PIBD cohort we will examine the relationship between PIBD age of onset, sex, ethnicity, and social deprivation and the 'any psychological condition' composite outcome.

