At the index date, we will define groups in the IBD case population based on mental health phenotype, including a comparator group without mental health comorbidity at the index date, and compare the sociodemographic characteristics of these groups.

Stream 2: Follow-up

We will then describe incidence of each study outcome in the five years after the index date for each group, and the relative incidence of each outcome in those with and without mental health comorbidity.

Stream 2: Study outcomes

These will comprise the following.

Quality of life indicators:

Affective symptoms (depression, low mood, deliberate self-harm, suicidal ideation or parasuicide), IBD symptoms, absence from school, absence from work, unemployment, substance abuse, and sleep problems. IBD symptoms will comprise; abdominal pain, discomforts or bloating, diarrhoea, weight loss, growth retardation and tiredness/fatigue. (See Appendix 1 – Table s1 for Read Codes and SNOMED codes).

IBD severity indicators:

Medication use, surgical intervention, nutritional supplement use, and markers of nutritional status. Surgical intervention will comprise any abdominal surgery, and stoma formation (as a separate outcome). Medication use will comprise use of: rectal 5-aminosalicylic acid (5-ASA), oral 5-ASA, rectal steroids, oral steroids, antimetabolites, tumour necrosis factor inhibitors (TNFi) and other biologic therapies. The latter of these groups may not be well captured in primary care and if so this will be reported in the limitations section of the final study manuscript. Nutritional supplements will comprise the five most prescribed nutritional supplements: Modulen, Fortisip, Ensure, Osmolite, and Neocate. Nutritional markers will comprise; being underweight (under the 5th centile of weight for height or BMI < 18.5 kg/m² after age 18) and growth retardation related codes. (See Appendix 1 – Table s2 for Read Codes and SNOMED codes).

Healthcare resource utilisation:

Primary care attendances and hospital admissions. Hospital admissions will be separated into general admissions (including those for IBD) and psychiatric admissions. (See Appendix 1 – Table s2 for Read Codes and SNOMED codes).

Stream 2: Statistical methods

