Read CTV3 Code	Term ID	Description
SNOMED Code	Term ID	Description

sTable 2.2 Algorithms used to identify anxiety episodes, depression episodes, and recurrent major depression. Expressions in capitals equate to Boolean expressions. *More than 1 year ago. SSRIs = selective serotonin reuptake inhibitors, TCA = tricyclic antidepressants, MAOI = monoamine oxidase inhibitors, CBT = cognitive behavioural therapy.

Clinical entity	Definition
Anxiety	Any coded anxiety episode AND concurrent treatment for anxiety
Depressive episode	Any coded depressive episode AND concurrent treatment for depression
Recurrent depressive disorder	(Any historical code* for a depressive episode AND current treatment for depression) OR Any code for recurrent depressive disorder
Anxiety treatments	SSRIs, anxiolytics, counselling, CBT, and psychotherapy
Depression treatments	SSRIs, TCAs, MAOIs, counselling, CBT, and psychotherapy

sTable 2.3 WHO International Statistical Classification of Diseases (ICD-10) for mental health conditions

Clinical entity	ICD 10 code	Definition
Depressive episode	F32	Any coded depressive episode AND concurrent treatment for depression
Recurrent depressive disorder	F33	(Any historical code* for a depressive episode AND current treatment for depression) OR Any code for recurrent depressive disorder
Depression treatments	NA	SSRIs, TCAs, MAOIs, counselling, CBT, and psychotherapy
Anxiety	F41	Any coded anxiety episode AND concurrent treatment for anxiety
Anxiety treatments	NA	SSRIs, anxiolytics, counselling, CBT, and psychotherapy
Self-harm	X60-X84	Any diagnostic or indicative code for any form of self-harm, including suicide attempt
Eating disorders	F50	Any diagnostic or indicative code for eating disorders

Body image disorders	F45.2	Any diagnostic or indicative code for body image / dysmorphic disorder (excluding hypochondriacal disorders not associated with body image)
Attention-deficit disorders	F90.0	Any diagnostic or indicative code for disturbance of activity and attention
Behavioural disorders	F91 F92	Any diagnostic or indicative code for conduct disorders
Adjustment disorders	F43.2	Any diagnostic or indicative code for adjustment disorders
Acute stress disorders	F43.0	Any diagnostic or indicative code for acute stress disorders
Post-traumatic stress disorder	F43.1	Any diagnostic or indicative code for Post-traumatic stress disorder

Appendix 3

sTable 3.1 Read and SNOMED codes to be used to identify quality of life

Depressive episode		

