219166007		Suicide or self injury by scalding (navigational concept)
225050000		Drowning self (finding)
219333004		Drowning or immersion of unknown intent (event)
418765005		Exposure to potentially harmful entity, undetermined intent (event)
219328003		Hanging, strangulation or suffocation of unknown intent (event)
219329006		Hanging of unknown intent (event)
219330001		Suffocation of unknown intent by plastic bag (event)
219342006		Injury of unknown intent by sharp instrument (disorder)
Absence from school		
Read V2 Code	Term ID	Description
E2C10	All	School refusal
E2D2z	All	School refusal
13Z4J	All	School attendance poor

Eu912	All	[X]Truancy from school
E2C10	All	Unsocial childhood truancy
E2C20	All	Socialised childhood truancy
Read CTV3 Code	Term ID	Description
X766A	All	School refusal
13Z4J	All	School attendance poor
X7667	All	Intentional non-attendance at school
13Z4G	All	Left school free will
X7669	All	Parental withholding from school
X7668	All	Truancy
XE1Yt	All	Unsocial childhood truancy
E2C20	All	Socialised childhood truancy
SNOMED Code	Term ID	Description
248050007		Intentional non-attendance at school (finding)
248052004		School refusal (finding)
105479008		Truancy (finding)
248051006		Parental withholding from school (finding)
161131005		Left school free will (finding)
161133008		School attendance poor (finding)
440680000		Unable to attend school due to illness (finding)
31492004		Fear of school (finding)
271947006		School phobia (finding)
Unemployment		
Read V2 Code	Term ID	Description
13J7.	All	Unemployed
13J70	All	Recently unemployed

Read CTV3 Code	Term ID	Description
13J7.	All	Unemployed
13J71	All	Chronic unemployment
ZV620	All	[V]Unemployment
13R..	All	Unemployment benefits
13R1.	All	Unemployment benefit
13R2.	All	Redundancy payment
13RZ.	All	Unemployment benefit NOS
13JX.	All	Time off work
13JG.	All	Voluntarily redundant
13J3.	All	Loss of job
13J30	All	Sacked from work
13J8.	All	Redundant
13JJ.	All	Unfit for work
13JJ0	All	Benefit agency reports unfit for work
13JJ1	All	Benefit agency reports unfit for work but fit note no longer required
13Jk.	All	Not in employment, education or training
9DG4.	All	IB 113 DLS incapacity for work form paid
9DG2.	All	IB 113 DLS incapacity for work form sent
9DG3.	All	IB 113 DLS incapacity for work form received
9DG1.	All	IB 113 DLS incapacity for work form completed
9DQ3.	All	ESA113 form paid
9DQ1.	All	ESA113 form sent
9DQ2.	All	ESA113 form received
9DQ0.	All	ESA113 form completed

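### The Parasuicide SNOMED list in sTable 3.1 counts six codes of unknown or undetermined intent, against the plan's own definitions and with no equivalent in its Read lists

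*Combined protocol and SAP*

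**What the plan says.** Table 1 (Stream 1) has two separate secondary outcomes. Self-harm is "Any coded episode of deliberate self-harm of any type". Suicide attempt is "Any episode of suicide attempt and suicide related codes, including deliberate medication overdose".

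Under Stream 2: Study outcomes, one quality-of-life indicator is "Affective symptoms (depression, low mood, deliberate self-harm, suicidal ideation or parasuicide". Quality of life is the primary objective of Stream 2.

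The codes for suicidal acts are in Appendix 3, in the table headed "sTable 3.1 Read and SNOMED codes to be used to identify quality of life", under Parasuicide. The SNOMED part of that block closes with six rows such as "Drowning or immersion of unknown intent (event", "Hanging, strangulation or suffocation of unknown intent (event" and "Exposure to potentially harmful entity, undetermined intent (event".

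The Table 1 footnote sends the reader to appendix tables for the mental health codes. sTable 2.1, which fills that role, has no block for self-harm or for suicide attempt. sTable 2.3 has one ICD-10 row for both, self-harm (X60-X84), defined as "Any diagnostic or indicative code for any form of self-harm, including suicide attempt".

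**The concern.** An outcome defined by deliberate intent should not be fed by codes that say the intent is not known. Stream 2 takes everyone with IBD aged under 25 at the index date and plans a 5 to under 12 age subgroup. At those ages an immersion, a suffocation or an injury from a sharp object may well be an accident.

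The second problem is uneven capture. The six rows exist only in SNOMED. The same injury could count for a patient whose record is in SNOMED and not for one whose record is in Read V2 or CTV3. The Stream 2 models adjust for age, gender, socioeconomic status, ethnicity and other childhood conditions, but not for practice or coding system. Stream 1 matches within practice only if numbers allow, so balance is not assured there either.

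At stake are one component of an indicator under the Stream 2 primary objective and, if the list is reused, a Stream 1 secondary outcome.

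**Working it through.** The plan gives no event count, event rate or sample size for these outcomes, so there is no figure to reproduce. The check compares the lists with the definitions.

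1. **SNOMED rows.** The Parasuicide block has 72 distinct SNOMED codes. I counted as unknown intent only rows whose description says so:
   - 219333004: drowning or immersion
   - 418765005: exposure to something potentially harmful
   - 219328003: hanging, strangulation or suffocation
   - 219329006: hanging
   - 219330001: suffocation by plastic bag
   - 219342006: injury by a sharp instrument

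   That is 6 / 72 = 8.3% of the codes, leaving 72 - 6 = 66. This is a share of codes, not of events.

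2. **Read rows.** No row in the Read V2 or CTV3 parts is described as being of unknown or undetermined intent. The three parts therefore do not define the same event.

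3. **Against the definitions.**

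| Definition | What it requires | Do the six rows meet it? |
|---|---|---|
| Table 1, self-harm | a deliberate act | No, intent is stated as not known |
| Table 1, suicide attempt | an attempt, a suicide-related code or a deliberate overdose | Not on their face |
| Stream 2, affective symptoms | among others, deliberate self-harm or parasuicide | No, except by being listed |
| sTable 2.3, self-harm | any form of self-harm, including suicide attempt | No, self-harm is not established |

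4. **Which outcomes the list feeds.** sTable 3.1 is headed for quality of life, so the link to the Stream 2 indicator is direct. For Stream 1 there are two possibilities. If the Parasuicide list is used, the six rows enter the suicide-attempt outcome. If it is not, the suicide-attempt outcome has no Read or SNOMED codes in the documents, because sTable 2.1 has no block for it. Either way the plan needs a statement.

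**The case against.** **The wording may be meant broadly.** Table 1 admits suicide-related codes, and the authors may have wanted undetermined intent included so as not to miss concealed attempts. That is a legitimate choice, but the documents do not state it, and the Read parts do not follow it.

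**In Stream 2 the effect may be slight.** The affective-symptoms indicator also takes in depression, low mood and self-harm. A patient already positive on one of those is unchanged by an unknown-intent code if the indicator is analysed as one binary event. This stands, and it limits the likely size. Overlap between self-harm and parasuicide is likewise harmless inside one indicator.

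Three stronger readings are tempting, and the documents do not support them:

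- **That the Stream 1 hazard ratio is attenuated by a known amount.** If a share f of recorded control events were unrelated to IBD, the observed ratio would be (1 - f) x HR + f. With f assumed at 10% to 30%, a true 2.0 becomes 0.9 x 2 + 0.1 = 1.9 down to 0.7 x 2 + 0.3 = 1.7. But f appears nowhere in the documents, the lack of any relation to IBD is itself assumed, and use of this list in Stream 1 is an inference. This is an illustration, not a demonstrated bias.
- **That self-harm and suicide attempt cannot be told apart.** The Parasuicide list does hold plain self-harm terms. But sTable 2.3 already makes self-harm the wider category, and nested outcomes can be reported separately. What is missing is a sentence carrying that nesting over to Table 1.
- **That the Read V2 list is faulty.** As extracted, 35 of its 122 rows have six characters, and the row for suicide reads 2... with four. The CTV3 part prints 33 of those 35 codes correctly with five characters. The lone 2... follows the U25 rows and fits a lost leading U. The extraction also garbles codes elsewhere: XSGom in sTable 2.1 appears as XGom in sTable 3.1. These are probably artefacts of reading the PDF and call only for a check against the source code file.

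**Conclusion.** The point holds for the six SNOMED rows. Applied as printed, the Parasuicide list counts injuries whose intent is recorded as unknown, and does so in SNOMED only. This bears directly on the Stream 2 affective-symptoms indicator. For the Stream 1 suicide-attempt outcome it is conditional on the list being used there.

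The extent is 6 of 72 SNOMED codes. Neither the size nor the direction of any bias in the relative incidence or hazard ratio can be derived from the documents. The conclusion rests on two things only: the printed descriptions of the six codes, and records reaching the database in more than one of the three coding systems that the plan lists. It does not establish that either outcome is mismeasured, only that the definition and the list disagree.

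**What to change.** 1. Remove 219333004, 418765005, 219328003, 219329006, 219330001 and 219342006 from the main parasuicide definition. Use them only in a sensitivity analysis that adds them back.
2. State which Read/SNOMED list Stream 1 uses for suicide attempt and for self-harm. If it is the Parasuicide list, apply the nesting of sTable 2.3: self-harm as the wider outcome, suicide attempt as an explicit subset, with the rows of that subset named.
3. Check the Read V2 Parasuicide rows against the source code file.

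The cost is an edit to the code list and one extra model run per affected outcome. The Stream 1 methods leave the extraction date to be confirmed, so the edit can be made first if extraction has not taken place. The downside is that a few true attempts coded as undetermined intent will appear only in the sensitivity analysis.

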To evaluate the magnitude of potential bias from including, as matched controls, people who are registered with GP practices but who do not attend their practice, we also repeated the primary analysis including only controls with a least one primary care consultation in the year preceding their index date.

All statistical analyses were performed using R statistical package software version 3.4.1. The study was conducted in line with the RECORD (Reporting of studies conducted using observational routinely collected data) guidelines.(13)

Stream 2:

Stream 2: Study design

The proposed study will use the retrospectively collected data of all eligible patients within the database at the date of data extraction. Within this primary care cohort, all patients with IBD will be identified using diagnostic codes and prescription records. A diagnostic algorithm will be developed to facilitate robust case identification of IBD and IBD subtypes as well as mental health outcomes.

Stream 2: Study cohort

The eligible IBD cases will comprise all prevalent cases of IBD aged under 25 at 01/01/2015 (index date) comprising of the three main subtypes; ulcerative colitis (UC), Crohn's disease (CD) and IBD unclassified (IBDU), excluding microscopic colitis, radiation induced enterocolitis and drug-induced enterocolitis. We will extract sociodemographic details for all individuals. Sociodemographic data will comprise by age group, age at diagnosis, sex, ethnicity, and socioeconomic status. Ethnicity will be categorised as follows to be consistent with the UK official census categories: White, Asian, Black African/Caribbean, Mixed, and Other. The index of multiple deprivation (IMD) will be used as a measure of socioeconomic status. This is derived from patient postcode at the point of data extraction.

We will identify comorbid psychological condition groups in all people with PIBD. These will comprise 3 composite phenotypes; anxiety/panic disorders, major depression or depressive episodes, and other psychological conditions. Other psychological conditions will be a composite of; eating disorders, body image disorder, attention-deficit disorder (ADHD), behavioural disorders, adjustment disorder, acute stress disorder, schizophrenia, bipolar disorder and post-traumatic stress disorder (PTSD). Where numbers are sufficient, subgroups of the broad 'other psychological conditions' composite may be examined.

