13OD.	All	Employment and support allowance

13J70	All	Recently unemployed
13J71	All	Chronic unemployment
ZV620	All	[V]Unemployment
XaPhf	All	Benefit agency reports unfit for work
Xabd4	All	Benefit agency reports unfit for work but fit note no longer required
13J8.	All	Redundant
13JG.	All	Voluntarily redundant
Ua2BD	All	Unfit to return to work
Ua2BE	All	Physically unfit for work
U12BF	All	Mentally unfit for work
13JX.	All	Time off work
XaZHu	All	ESA113 form paid
XaZHt	All	ESA113 form sent
XaZHs	All	ESA113 form received
XaZHj	All	ESA113 form completed
XaBhC	All	Employment and support allowance
XacJr	All	Not in employment, education or training
XE0pT	All	Loss of job
Ua0V9	All	Dismissed from job
Ua0VA	All	Unfair dismissal from job
XaCIW	All	IB 113 DLS incapacity for work form paid
XaCIU	All	IB 113 DLS incapacity for work form sent
XaCIV	All	IB 113 DLS incapacity for work form received
XaCIT	All	IB 113 DLS incapacity for work form completed
13JJ.	All	Unfit for work
13J6.	All	Medically retired

SNOMED Code	Term ID	Description
266956001		Loss of job (finding)
105496009		Dismissed from job (finding)
160901009		Made redundant (finding)
73438004		Unemployed (finding)
160900005		Chronic unemployment (finding)
160899000		Recently unemployed (finding)
354581000000101'		Unemployed person (person)
719401000000102'		Unemployed person (qualifier value)
224474004		Unfair dismissal from job (finding)
105498005		Voluntarily redundant (finding)
723481000000104'		Youth unemployment (qualifier value)
161005005		Unemployment benefits (qualifier value)
161006006		Unemployment benefit (qualifier value)
723971000000106'		Long term unemployment (qualifier value)
313083007		Unemployment counseling (procedure)
313084001		Redundancy counseling (procedure)
281559009		Number of days off work (observable entity)
160928004		Amount of time off work (observable entity)
439907006		Number of sick days off work in last month (observable entity)
105495008		Forced retirement, life event (finding)
925481000000108'		Benefits agency reports unfit for work but fit note no longer needed (finding)
161007002		Redundancy payment (qualifier value)
160910001		Unfit for work (finding)
374171000000109'		Benefits agency reports unfit for work (finding)
304248001		Unfit for particular post (finding)

22588002		Unfit to return to work (finding)
22589001		Mentally unfit to return to work (finding)
225889005		Physically unfit to return to work (finding)
224384002		Registered with job center (finding)

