224385001		Registered with work placement officer (finding)
14121000000104'		IB113 DLS Incapacity for work form sent (finding)
14141000000106'		IB113 DLS Incapacity for work form paid (finding)
14131000000102'		IB113 DLS Incapacity for work form received (finding)
14111000000105'		IB113 DLS Incapacity for work form completed (finding)
835611000000109'		Employment and support allowance status (finding)
835641000000105'		Employment and support allowance 113 form completed (finding)
835711000000103'		Employment and support allowance 113 form paid (finding)
835691000000100'		Employment and support allowance 113 form received (finding)
835671000000104'		Employment and support allowance 113 form sent (finding)
957481000000103'		Not in employment, education or training (finding)
Absence from work		
Read V2 Code	Term ID	Description
Read CTV3 Code	Term ID	Description
SNOMED Code	Term ID	Description
IBD symptoms - abdominal pain		
Read V2 Code	Term ID	Description
Read CTV3 Code	Term ID	Description
SNOMED Code	Term ID	Description
IBD symptoms - discomforts or bloating		
Read V2 Code	Term ID	Description
Read CTV3 Code	Term ID	Description

SNOMED Code	Term ID	Description
IBD symptoms - diarrhoea		
Read V2 Code	Term ID	Description
Read CTV3 Code	Term ID	Description
SNOMED Code	Term ID	Description
IBD symptoms - weight loss		
Read V2 Code	Term ID	Description
Read CTV3 Code	Term ID	Description
SNOMED Code	Term ID	Description
IBD symptoms - tiredness/fatigue		
Read V2 Code	Term ID	Description
Read CTV3 Code	Term ID	Description
SNOMED Code	Term ID	Description
Growth retardation related codes		
Read V2 Code	Term ID	Description
Read CTV3 Code	Term ID	Description
SNOMED Code	Term ID	Description

sTable 3.2 Read and SNOMED codes to be used to identify the severity of IBD

Medication use		
Read V2 Code	Term ID	Description
Read CTV3 Code	Term ID	Description
SNOMED Code	Term ID	Description
Surgical intervention		
Read V2 Code	Term ID	Description
Read CTV3 Code	Term ID	Description
SNOMED Code	Term ID	Description
Hospital admissions		
Read V2 Code	Term ID	Description
Read CTV3 Code	Term ID	Description
SNOMED Code	Term ID	Description
Nutritional supplements (Modulen, Fortisip, Ensure, Osmolite, and Neocate)		
Read V2 Code	Term ID	Description
Read CTV3 Code	Term ID	Description
SNOMED Code	Term ID	Description

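### Five codes for time or sick days off work are listed under unemployment, a separate indicator from absence from work, and the unemployment rate counts person-time below working age

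*Combined protocol and SAP*

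**What the plan says.** Quality-of-life indicators are the primary objective of Stream 2. The section on Stream 2 study outcomes lists, after affective and IBD symptoms, "absence from school, absence from work, unemployment, substance abuse, and sleep problems". Work absence and unemployment are therefore two outcomes.

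The Unemployment block of Appendix 3, sTable 3.1 contains, besides codes for job loss, redundancy and unemployment benefit:

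- Read code 13JX. (time off work), which appears twice;
- SNOMED 281559009, "Number of days off work (observable entity";
- SNOMED 160928004, "Amount of time off work (observable entity";
- SNOMED 439907006, "Number of sick days off work in last month (observable entity";
- rows on fitness for work, such as "Unfit for work (finding" and "Unfit to return to work (finding";
- rows for incapacity forms and ESA, such as "IB113 DLS Incapacity for work form sent (finding".

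The absence-from-work block that follows has column headers and no codes.

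The Stream 2 cohort is "all prevalent cases of IBD aged under 25 at 01/01/2015 (index date"), with no lower limit. The Stream 2 statistical methods include everyone with at least six months of follow-up and use log person-years as the offset. They adjust for age and, where numbers allow, report incidence in age bands that start at 5 and have a cut at 16. Neither work outcome is restricted to people of working age.

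**The concern.** A record of sick days taken last month describes someone who has a job to be absent from. Counting it as unemployment reverses its plain meaning. Mental illness plausibly raises sickness absence directly, so an excess of such records in the mental health groups could be reported as an excess of job loss. Covariate adjustment cannot repair an outcome that is wrongly defined.

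The age point is separate. Young children cannot become unemployed, yet their follow-up enters the denominator. The plan promises incidence by mental health phenotype, so the absolute unemployment figures would be too low. Crude comparisons would also be distorted if the phenotype groups differ in age.

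**Working it through.** The plan gives no sample size, power or unemployment rate, so there is no stated figure to reproduce.

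**1. Row count.** Input: the Unemployment block of sTable 3.1, with Read V2 and CTV3 taken together (the boundary between them may have been disturbed in the PDF text) and repeats kept. Rows were classed by their description.

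| Class | Read | SNOMED | All |
|---|---|---|---|
| Time or sick days off work | 2 | 3 | 5 |
| Unfit for work | 9 | 7 | 16 |
| Incapacity form or ESA | 18 | 9 | 27 |
| Retired | 1 | 1 | 2 |
| Unemployment, job loss, other | 23 | 20 | 43 |
| Total | 53 | 40 | 93 |

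The five clear rows are 5/93 = 5% of the list. The ambiguous rows are 16 + 27 = 43, or 43/93 = 46%. These are shares of rows, not of events.

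**2. Effect of mixing the two outcomes (all values assumed).** Let a be the true unemployment rate ratio, b the absence rate ratio, and f the share of comparator-group events that come from absence codes. The reported ratio is a(1-f) + bf. With a = 1.0 and b = 2.0:

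- f = 0.25: 0.75 + 0.50 = 1.25
- f = 0.50: 0.50 + 1.00 = 1.50

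This shows the direction and form of the error. It does not predict its size, because neither b nor f can be taken from the documents.

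**3. Absolute rate.** Let s be the share of person-years below working age, and assume no unemployment events there. The overall rate equals the working-age rate times (1-s), so it is understated by 1/(1-s):

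- s = 0.2: 1/0.8 = 1.25
- s = 0.3: 1/0.7 = 1.43
- s = 0.4: 1/0.6 = 1.67

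**4. Relative incidence.** If the true ratio is 1, the crude ratio is (1-s1)/(1-s0), where s1 is the share in the mental health group and s0 the share in the comparator. With s1 = 0.10, s0 = 0.30 gives 0.90/0.70 = 1.29, and s0 = 0.40 gives 0.90/0.60 = 1.50. For the second case a Poisson model was fitted to expected counts in the plan's four age bands. The assumed person-year shares were 5, 5, 20 and 70% in the mental health group and 15, 25, 20 and 40% in the comparator, with a rate of 0 below 16 and 0.05 per year above. The crude ratio of 1.50 fell to 1.03 with linear age in the model, and to 1.00 when restricted to age 16 and over with age bands.

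**5. Code validity.** The SNOMED (Verhoeff) check digit was tested on all 40 SNOMED codes in the block. Two fail as printed, 22588002 and 22589001, both in the unfit-for-work class; the other 38 pass. The nine-digit numbers 225888002 and 225890001 both pass, so a lost digit is a plausible cause.

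**The case against.** The case for leaving the list alone rests on four arguments.

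- **The clear error is small.** Only five rows are unambiguous. A reader might add the 43 unfit, incapacity and ESA rows, reach 48 of 93 (52%), and infer that the indicator would mostly measure sickness certification. The documents do not support that. Rows repeat one concept across code systems and across form stages (sent, received, completed, paid), and no recording frequencies are given. This objection stands.
- **The ambiguous rows may belong where they are.** Someone on ESA or judged unfit for work may have no job. The plan defines neither indicator, so assigning all these rows to absence from work could create the opposite misclassification. This also stands; what is missing is a stated rule.
- **Absence from work need not lose events.** It is tempting to say that its events have been taken by unemployment. But its list is blank, nothing makes the lists exclusive, and sTable 2.1 puts some codes in two lists (E2003 and Eu412 under both depression and anxiety). A loss cannot be shown. Double listing would still leave employed people counted as unemployed.
- **Age is already handled.** The models adjust for age, and bands split at 16 are planned where numbers allow. This largely answers the concern for adjusted relative incidence. It does not answer it for the overall absolute rate, and the age-specific results are conditional on numbers.

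On the two failing codes, a reader might conclude that they would retrieve nothing. The printed text cannot distinguish an error in the plan from a digit lost in PDF reading.

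**Conclusion.** The point holds in a limited form. Five rows that record absence from a job sit under unemployment although absence from work is a separate indicator, and following the list would misclassify employed people. The resulting bias cannot be sized from the documents; the ratios of 1.25 to 1.50 in step 2 depend wholly on assumed inputs. The 43 unfit, incapacity and ESA rows are unresolved rather than wrong.

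The overall absolute unemployment rate is understated by 1.25 to 1.67 if 20 to 40% of person-time is below working age. That share is an assumption, as is the absence of events below that age; the threshold of 16 is borrowed from the plan's own age bands. Adjusted relative incidence should be little affected, provided age is modelled adequately; the plan does not state its functional form.

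Unemployment is one of seven quality-of-life indicators, so this affects one component of the Stream 2 primary objective, not the whole of it. It is worth correcting before extraction.

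**What to change.** 1. Move the five time-off and sick-day rows to absence from work, complete that blank list, and add a one-sentence definition of each work indicator.
2. Put the 16 unfit rows and the 27 incapacity-form and ESA rows in a separate group for unfitness for work or incapacity, or analyse unemployment with and without them. Do not transfer them wholesale.
3. Count person-time for both work outcomes only from age 16, and for school absence only during a pre-specified school age. Someone who turns 16 during follow-up enters the work-outcome denominator on that date.
4. Check 22588002 and 22589001 against the terminology source.

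The records are retrospective, so no new data are needed: the work is re-sorting one list and adding an age filter. The cost is fewer unemployment events, hence less precision for that indicator, and a little more coding.
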